## **2.0 TRIAL DESIGN**

### **2.1 Trial Design**

This is a multicenter, nonrandomized, multi-cohort trial of MK-3475 in subjects with advanced solid tumors. Subjects will be enrolled into Cohort A for triple negative breast cancer (TNBC), Cohort B for the initial head and neck (H/N) cancer cohort and Cohort B2 for the H/N cancer expansion cohort, Cohort C for urothelial tract cancer, or Cohort D for gastric cancer. Only subjects with PD-L1 positive tumors will be enrolled in Cohorts A, B, C and D. Subjects in Cohort B2 may be enrolled regardless of PD-L1 status. Approximately 114 subjects were planned to be enrolled in Cohorts A, B, C and D of this trial to examine the safety and efficacy of MK-3475 in these populations. Approximately 110 subjects will be enrolled into Cohort B2 of the study to further explore the safety and efficacy in the head and neck cancer population at a different dose and schedule of MK-3475 and including both PD-L1 positive and negative subjects. Subjects enrolled in Cohorts A, B, C and D will receive 10 mg/kg of MK-3475 administered every 2 weeks. Subjects enrolled in Cohort B2 will receive 200 mg of MK-3475 administered every 3 weeks. Subjects will be evaluated every 8 weeks (56 days  $\pm$  7 days) with radiographic imaging to assess response to treatment. RECIST 1.1 response rate as assessed by independent central radiology review will be used as the primary efficacy endpoint for Cohorts A, B, C and D. RECIST 1.1 response rate as assessed by independent central radiology review will be used as the primary efficacy endpoint for Cohort B2. RECIST 1.1 will be adapted as described in Section 4.2.3.1 to accommodate for the tumor response patterns seen with MK-3475 treatment (e.g., tumor flare), and this adapted RECIST will be used by the sites for treatment decisions in all cohorts. Adverse events will be monitored throughout the trial and graded in severity according to the guidelines outlined in the NCI Common Terminology Criteria for Adverse Events (CTCAE) version 4.0. Treatment with MK-3475 will continue until documented disease progression, unacceptable adverse event(s), intercurrent illness that prevents further administration of treatment, investigator's decision to withdraw the subject, subject withdraws consent, pregnancy of the subject, noncompliance with trial treatment or procedure requirements, completion of 24 months of treatment with MK-3475, or administrative reasons. Subjects who attain an investigator-determined confirmed complete response (CR) may consider stopping trial treatment after receiving at least 24 weeks of treatment. Subjects who discontinue after at least 24 months of therapy for reasons other than disease progression or intolerability or who discontinue after attaining a CR may be eligible for up to one year of retreatment after they have experienced radiographic disease progression. The decision to retreat will be at the discretion of the investigator only if no cancer treatment was administered since the last dose of MK-3475, the subject still meets the safety parameters listed in the Inclusion/Exclusion criteria and the trial remains open (refer to Section 7.1.5.2.1 for further details). After the end of treatment, each subject will be followed for 30 days for adverse event monitoring (serious adverse events will be collected for 90 days after the end of treatment or 30 days after the end of treatment if the subject initiates new anticancer therapy, whichever is earlier). Subjects who discontinue treatment for reasons other than disease progression will have post-treatment follow-up for disease status until disease progression, initiating a non-study cancer treatment, withdrawing consent,

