- (8) **Objective:** To evaluate the progression-free survival (PFS) in subjects with advanced solid tumors receiving MK-3475.
- (9) **Objective:** To evaluate the overall survival (OS) in subjects with advanced solid tumors receiving MK-3475.
- (10) **Objective:** To evaluate the response duration in subjects with advanced solid tumors receiving MK-3475.

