#### **7.1.2.5.3 Tumor Imaging During Trial**

Tumor imaging may be performed by CT or magnetic resonance imaging (MRI), but the same imaging technique should be used in a subject throughout the trial. Imaging should be performed every 8 weeks (56 days  $\pm$  7 days) from the first dose of trial treatment or more frequently if clinically indicated. Imaging should not be delayed for delays in cycle starts or extension of MK-3475 cycle intervals.

Per RECIST 1.1, response should be confirmed by a repeat radiographic assessment not less than 4 weeks from the date the response was first documented. The scan for confirmation of response may be performed at the earliest 4 weeks after the first indication of response, or at the next scheduled scan (8 weeks later), whichever is clinically indicated.

Imaging should continue to be performed until documented disease progression, the start of new anti-cancer treatment, withdrawal of consent, death, or the end of the study, whichever occurs first. Disease progression should be confirmed at least 4 weeks after the first scan indicating progressive disease in clinically stable subjects. Subjects who have unconfirmed disease progression may continue on treatment until progression is confirmed provided they have met the conditions detailed in Section 7.1.2.5.1.

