Overall RECIST 1.1 response rate based on investigator assessment for cohorts A,B, C and D	Exact methods for binomial parameter	FAS	Subjects with missing data are considered non-responders
Overall RECIST 1.1 response rate based on investigator assessment for Cohort B2	Exact methods for binomial parameter	FAS	Subjects with missing data are considered non-responders
Progression-free survival	Summary statistics using Kaplan-Meier method	FAS	Censored at last assessment
Overall survival	Summary statistics using Kaplan-Meier method	FAS	Censored at last assessment
Response duration	Summary statistics using Kaplan-Meier method	All responders	Non-responders are excluded in analysis
‡ For Cohort D, the analyses for the Asia Pacific (AP) population will be performed as appropriate.			

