### **8.2.3.1 Efficacy/Immunogenicity/Pharmacokinetics Endpoints**

Efficacy and safety endpoints that will be evaluated for are listed below, followed by the descriptions of the derivations of selected endpoints.

The primary efficacy endpoint is response rate, defined as the proportion of subjects in the analysis population who have complete response (CR) or partial response (PR) using RECIST 1.1 criteria at any time during the study. Response for the primary analysis for cohorts A, B, C, D and B2 will be determined by a central independent radiology review. Secondary analyses will be based on the responses as assessed by the investigator.

Key secondary efficacy endpoints include:

- RECIST 1.1 response rate among HPV positive subjects.
- Response rate based on site assessments using RECIST 1.1.

Other secondary efficacy endpoints include: (1) duration of response, defined as time from first RECIST 1.1 response to disease progression in subjects who achieve a PR or better; (2) progression-free survival (PFS), defined as the time from allocation to the first documented disease progression according to RECIST 1.1 or death due to any cause, whichever occurs first; and (3) overall survival (OS).

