## **8.2.4 Analysis Populations**

### **8.2.4.1 Efficacy Analysis Populations**

The Full Analysis Set (FAS) population will serve as the primary population for the analysis of efficacy data in this study. The FAS population consists of all randomized subjects in each Cohort who:

- Receive at least one dose of study treatment,
- Have a baseline scan with measurable disease per RECIST 1.1 by independent central radiology review, and
- Have a post baseline scan OR discontinue the trial due to progressive disease/drug related AE

For secondary by Investigator assessment, measurable disease for inclusion in the FAS population will be defined using Investigator assessment of the baseline scan.

A supportive analysis using the All Subjects as Treated (ASaT) population, defined as all randomized subjects, who received at least one dose of study treatment, will be performed for the primary efficacy endpoint(s).

Subjects will be included in the treatment group to which they are randomized for the analysis of efficacy data. Details on the approach to handling missing data are provided in Section 8.2.5 Statistical Methods.

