Overall RECIST 1.1 response rate based on based on independent central radiology review, for subjects previously treated with cetuximab and platinum in Cohorts B and B2	Exact test of binomial parameter	FAS (Primary) ASaT (Supportive)	Subjects with missing data are considered non-responders
Overall RECIST 1.1 response rate based on investigator assessment for cohorts A,B, C and D	Exact methods for binomial parameter	FAS (Primary) ASaT (Supportive)	Subjects with missing data are considered non-responders
Overall RECIST 1.1 response rate based on investigator assessment for Cohort B2	Exact methods for binomial parameter	FAS (Primary) ASaT (Supportive)	Subjects with missing data are considered non-responders

Endpoint/Variable‡ (Description, Time Point)	Statistical Method	Analysis Population	Missing Data Approach
Progression-free survival	Summary statistics using Kaplan-Meier method	FAS(Primary) ASaT (Supportive)	Censored at last assessment
Overall survival	Summary statistics using Kaplan-Meier method	FAS(Primary) ASaT (Supportive)	Censored at last assessment
Response duration	Summary statistics using Kaplan-Meier method	All responders	Non-responders are excluded in analysis

The strategy to address multiplicity issues with regard to multiple efficacy endpoints is described in Section 8.2.6, Multiplicity and Section 8.2.9, Interim Analyses.

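### The primary overall survival analysis uses a population defined partly by events after Day 1, so some known early deaths can drop out of it

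*Combined protocol and SAP*

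**What the plan says.** Secondary objective 9 (protocol section 3.2) is "To evaluate the overall survival (OS) in subjects with advanced solid tumors receiving MK-3475". The SAP lists the endpoint only as "and (3) overall survival (OS") in section 8.2.3.1, with no definition and no time origin; PFS, by contrast, runs from allocation. The planned method in Table 9 (section 8.1.1) is "Summary statistics using Kaplan-Meier method".

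The places that set the population for OS do not agree:

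- Table 11 (section 8.2.5.1), OS row: "FAS (Primary) ASaT (Supportive").
- Table 9 (section 8.1.1), OS row: FAS only, although the text above the table promises supportive efficacy analyses in the ASaT in general terms.
- Section 8.2.4.1: the supportive ASaT analysis is described for the primary efficacy endpoint(s) only.

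The FAS in section 8.2.4.1 requires at least one dose and two further conditions. One is fixed at baseline: "Have a baseline scan with measurable disease per RECIST 1.1 by independent central radiology review, and". The other is settled afterwards: "Have a post baseline scan OR discontinue the trial due to progressive disease/drug related AE". Section 2.1 schedules imaging at 8-week intervals ("Subjects will be evaluated every 8 weeks"), and section 7.1.2.5.3 allows scans "from the first dose of trial treatment or more frequently if clinically indicated".

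The ASaT needs only allocation and one dose. Section 2.1 provides telephone survival follow-up for all subjects, scanned or not.

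**The concern.** OS can be observed without a scan and without measurable disease. Making membership of the OS population depend on a scan that is normally due at Week 8, while the clock starts at or near Day 1, introduces immortal time: a subject admitted only through a scan cannot have died before it. Death itself is not a route into the FAS. An unscanned subject who dies early of an unrelated cause, or whose reason for stopping is recorded simply as death, is removed together with the event that OS is meant to count.

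Three features of the text add to the problem.

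- The FAS wording speaks of leaving the trial because of progression, whereas section 5.8 lists progression as a reason to stop treatment. Read literally, this narrows the PD route.
- Section 5.9 allows extra enrolment to reach the evaluable number and protects only PD and drug-related-event discontinuations from replacement. An unscanned early death could be replaced by a subject who is scanned.
- Section 8.2.5.1 censors at Day 1 any subject lacking efficacy evaluation or survival data. The sentence follows the PFS text, but nothing says that it stops there.

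At stake are the OS curve and median that the trial reports as primary.

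**Working it through.** **Plan's own figure.** The documents give no OS median, rate, event count or power, so there is none to reproduce. The only stated figures that bear on how many subjects the FAS may lose are the Cohort B2 numbers: about 110 enrolled and 100 evaluable. The response-rate power attached to those 100 does reproduce: for 11/100 or more, the exact binomial gives 0.0115 at a true rate of 5% and 0.994 at 20%, against a stated >99%.

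**Direction.** Let f be the share of treated subjects removed because they died unscanned, outside the two admitted reasons, before Week 8. Removing them deletes deaths and no survivors, so after Week 8

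S_FAS(t) = S(t)/(1 − f), which is never below S(t).

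With exponential survival and true median m, median_FAS = m × log2[2/(1 − f)].

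**Illustration 1: assumed early-death share.** From the plan: first scheduled scan at 56 days, L = 56/30.4375 = 1.84 months. Assumed: exponential OS, m = 6 to 12 months, and a share q = 25% or 50% of deaths before Week 8 excluded. Then d = 1 − 2^(−L/m) and f = q × d.

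| m (months) | d | q | f | 6-month OS, true → FAS | FAS median (months) |
|---|---|---|---|---|---|
| 6 | 19.1% | 25% | 4.8% | 50.0% → 52.5% | 6.42 |
| 6 | 19.1% | 50% | 9.6% | 50.0% → 55.3% | 6.87 |
| 12 | 10.1% | 25% | 2.5% | 70.7% → 72.5% | 12.44 |
| 12 | 10.1% | 50% | 5.0% | 70.7% → 74.5% | 12.90 |

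For example, 0.500/(1 − 0.048) = 0.525. The bounds are q = 0, with no bias, and q = 100%, where the median rises by the full 1.84 months.

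**Illustration 2: Cohort B2's own allowance.** At most 10 of 110 subjects (9.1%) are allowed for as non-evaluable for any reason. If k of the 10 are early deaths and the rest are unrelated to survival, the later curve is multiplied by 110/(110 − k). For an assumed true median of 8 months (true 12-month OS 35.4%):

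- k = 2: factor 1.019, median 8.21 months, 12-month OS 36.0%
- k = 5: factor 1.048, median 8.54 months, 12-month OS 37.0%
- k = 10: factor 1.100, median 9.10 months, 12-month OS 38.9%

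For Cohorts A to D no allowance can be inferred: the evaluable targets 26 + 22 + 12 + 22 + 32 = 114 equal the planned enrolment.

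**The case against.** The strongest reply is that an unconditioned estimate is already planned: Table 11 lists ASaT as supportive for OS, so the issue is only which estimate is called primary. That would carry more weight if section 8.2.4.1 and Table 9 agreed with Table 11. They do not, so the safeguard is not secure.

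Other parts of the reply stand and limit the point.

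- A reader might infer that no early death can appear in the FAS curve. That is wrong. Discontinuations for PD or a drug-related event enter without a scan, and earlier scans are allowed if clinically indicated. Flow-chart notes y (section 6.1) and v (section 6.2) also ask for a scan when therapy stops without confirmed progression, unless one was done in the previous 4 weeks.
- A reader might take the illustrated sizes as estimates. They are not. The 25-50% share is assumed, and the plan's separate handling of cancer progression makes the PD route a natural one for cancer deaths. Entry requires ECOG 0 or 1 and adequate organ function, so early hazard may be below constant. The top case removes 9.6% of treated subjects, more than Cohort B2's whole allowance of 9.1%.
- A reader might infer that OS is to be judged against historical survival. The plan sets historical comparators for response rate only.
- A reader might infer that OS is overstated on balance. The FAS also drops subjects without centrally measurable disease; that is a baseline condition creating no immortal time, and their prognosis is unknown. Only the early-death component has a known direction.
- The effect is within sampling error. At 50% survival without censoring, 1.96 × √(0.25/n) is 21 points for n = 22, 17 for n = 32 and 10 for n = 100. This does not excuse a bias that can be removed by wording, but it bears on priority.

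**Conclusion.** The point holds in a limited form. The primary OS population is selected partly on events after Day 1, and a treated subject who dies unscanned for a reason recorded as neither PD nor a drug-related event is lost from it despite a known death. That exclusion can only raise the curve.

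The size is unknown, with a lower bound of zero. Under the stated assumptions (exponential OS, median 6 to 12 months, a quarter to a half of deaths before Week 8 excluded), it is about 0.4-0.9 months on the median and 2-5 points on 6-month OS.

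OS is a secondary descriptive endpoint with no hypothesis, alpha or sample-size basis. No test or success criterion is affected; the reported curve and median are. It should be corrected, but it does not threaten the trial's primary conclusions.

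**What to change.** 1. In the OS rows of Tables 9 and 11, make ASaT the primary population, with every treated subject at risk from first dose, and keep the FAS as supportive. Add this time origin to section 8.2.3.1, where OS has none.
2. Extend the ASaT analysis in section 8.2.4.1 beyond the primary efficacy endpoint(s), so that it covers OS and agrees with the tables.
3. State in section 8.2.5.1 that the Day 1 censoring sentence does not apply to OS for subjects with known survival status. Otherwise an unscanned early death could contribute nothing even in the ASaT.

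The difference between the FAS wording on leaving the trial and section 5.8 on stopping treatment should also be reconciled, since the supportive FAS analysis depends on it.

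The cost is SAP wording. The ASaT analysis of OS is already listed in Table 11, survival follow-up already covers all subjects, and no new data are needed.

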### **8.2.5.2 Statistical Methods for Safety Analyses**

Safety and tolerability will be assessed by clinical review of all relevant parameters including adverse experiences (AEs), laboratory tests, and vital signs.

Summary statistics (counts, percentage, mean, standard deviation, etc.) will be provided for the safety endpoints as appropriate. The 80% confidence interval for the incidence rate of Grade 2 or higher adverse events with an immune etiology and the incidence rate of Grade 4/5 AEs will be provided as appropriate.

### **8.2.5.3 Summaries of Baseline Characteristics, Demographics, and Other Analyses**

#### **8.2.5.3.1 Demographic and Baseline Characteristics**

Baseline characteristics will be assessed by the use of tables and/or graphs for each cohort. No statistical hypothesis tests will be performed on these characteristics. The number and percentage of subjects screened, randomized, the primary reasons for screening failure, and the primary reason for discontinuation will be displayed. Demographic variables (e.g., age, gender), baseline characteristics, primary and secondary diagnoses, and prior and concomitant therapies will be summarized by treatment either by descriptive statistics or categorical tables.

### **8.2.6 Multiplicity**

The false positive rate for testing the primary efficacy endpoint in each cohort (Cohort A, Cohort B, Cohort C, Cohort D, and Cohort B2) is controlled at 0.025 (1-sided) for each cohort.

If the primary hypothesis in Cohort B2 is successful, then  $\alpha=0.025$  (1-sided) will be passed to the secondary evaluation of subjects in Cohort B and Cohort B2 with prior exposure to cetuximab and platinum therapy in a step down approach.

### **8.2.7 Sample Size and Power Calculations**

The calculation of power and sample size for each cohort does not account for interim analysis. Cohort A (triple negative breast cancer subjects): With approximately 26 evaluable PD-L1 positive subjects with triple negative breast cancer, the study has approximately 80% power to detect a 25% difference in ORR under the null hypothesis of ORR=20% with a type I error rate of 2.5% if the true ORR is 45%. The null hypothesis rate of 20% is based on the historic response rate in large phase III trials for standard single agent chemotherapy in 2nd line breast cancer utilizing WHO-based bi-dimensional responses [34, 35, 36]. Success for this hypothesis requires at least 10/26 responses. The actual number of subjects enrolled may be larger than 26 to ensure that at least 26 subjects are evaluable for analysis.

Cohort B (head and neck cancer subjects): HPV negative head and neck cancer subjects will be evaluated separately from HPV positive head and neck cancer subjects. With a maximum of 22 evaluable PD-L1 positive subjects with HPV negative head and neck cancer, the study has approximately 80% power to detect a 25% difference in ORR under the null hypothesis of ORR=10% with a type I error rate of 2.5% if the true ORR is 35%. Success for this hypothesis requires at least 6/22 responses. The actual number of subjects enrolled may be larger than 22 to ensure that at least 22 subjects are evaluable for analysis.

With a maximum of 12 evaluable PD-L1 positive subjects with HPV positive head and neck cancer, the study has approximately 73% power to detect a 35% difference in ORR under the null ORR=20% with a type I error rate of 5% if the true ORR is 55%. The null hypothesis rate of 20% is based on historic response of chemotherapy in head and neck cancer trials [37, 38]. Success for this hypothesis requires at least 6 responses. The actual number of subjects enrolled may be larger than 12 to ensure that at least 12 subjects are evaluable for analysis. However, if 6 responses are observed prior to 12 subjects with HPV positive head and neck cancer enrolling in the trial, enrollment may be stopped in this group as the hypothesis success criterion will have been reached.

Cohort C (urothelial tract cancer subjects): With a maximum of 22 evaluable PD-L1 positive subjects with urothelial tract cancer, the study has approximately 80% power to detect a 25% difference in ORR under the null hypothesis of ORR=10% with a type I error rate of 2.5% if the true ORR is 35%. The null hypothesis rate of 10% is based on the historic response rate of single agent pemetrexed (RR 6%) or vinflunine (RR 9%) chemotherapy for bladder cancer [39, 40]. Success for this hypothesis requires at least 6/22 responses. The actual number of subjects enrolled may be larger than 22 to ensure that at least 22 subjects are evaluable for analysis.

Cohort D (gastric cancer subjects): With a maximum of 32 evaluable PD-L1 positive subjects with gastric cancer, stratified to include 16 Asia Pacific (AP) and 16 non-AP, the study has approximately 90% power to detect a 25% difference in ORR under the null hypothesis of ORR=15% with a type I error rate of 2.5% if the true ORR is 40%. Success for this hypothesis requires at least 10/32 responses. A total of 16 AP subjects will provide approximately 80% power with type I error rate of 0.1 to detect a 25% difference in ORR under the null hypothesis of ORR=15% if the true ORR is 40%. At least 4/16 responses will

be needed to claim the success of this hypothesis for the AP population. The null hypothesis rate of 15% is based on the response rate in large ( $n > 100$ ), trials for standard of care chemotherapy irinotecan/mFOLFIRI (RR 12%), and irinotecan/docetaxel (RR 13%) for 2nd line metastatic gastric cancer [28, 29]. The actual number of subjects enrolled may be larger than 32 to ensure that at least 32 subjects are evaluable for analysis.

Cohort B2 (head and neck cancer subjects, expansion cohort): With 100 evaluable subjects in Cohort B2, the study provides >99% power to detect a 15% difference in ORR under the null hypothesis of ORR=5% with a type I error rate of 2.5% if the true ORR is 20%. Success for this hypothesis requires at least 11/100 responses. The null hypothesis rate of 5% is based on historic response of chemotherapy in head and neck cancer trials [37]. The actual number of subjects enrolled may be larger than 100 to ensure at least 100 subjects are evaluable for analysis.

Cohorts B and B2 previously treated with cetuximab and platinum: With 60 evaluable head and neck cancer subjects previously treated with cetuximab and platinum, the study has 93% power to detect a 15% difference in ORR under the null hypothesis of ORR=5% with a type I error rate of 2.5% if the true ORR is 20%. Success for this hypothesis requires at least 8/60 responses. The null hypothesis rate of 5% is based on historic response of chemotherapy in head and neck cancer trials [37].

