#### **5.1.2 Subject Inclusion Criteria**

In order to be eligible for participation in this trial, the subject must:

1. Be willing and able to provide written informed consent/assent for the trial. The subject may also provide consent/assent for Future Biomedical Research. However, the subject may participate in the main trial without participating in Future Biomedical Research.
2. Be  $\geq$  18 years of age on day of signing informed consent.

3. Have histologically or cytologically-confirmed diagnosis of cancer that is recurrent, metastatic, or persistent and meet the following corresponding requirements for the cohort of the study they will enroll into. There is no limit to the number of prior treatment regimens.
  - a. Cohort A: Have diagnosis of triple negative breast cancer (Estrogen, Progesterone, and HER2 negative carcinoma of the breast)
  - b. Cohort B and B2: Have a diagnosis of squamous cell carcinoma of the head and neck

Note: A subset of subjects enrolled to Cohort B known to have HPV positive head and neck squamous cell cancer will be assessed.

Note: Cohort B2 will enroll both HPV positive and HPV negative subjects
  - c. Cohort C: Have a diagnosis of urothelial tract cancer of the renal pelvis, ureter, bladder, or urethra. Both transitional cell and non-transitional cell histologies are allowed.
  - d. Cohort D: Have a diagnosis of adenocarcinoma of the stomach or gastro-esophageal junction
4. Have provided tissue for biomarker analysis from an archival tissue sample or newly obtained core or excisional biopsy of a tumor lesion not previously irradiated. (Subjects with H/N cancer may provide tissue from a previously irradiated lesion.)
5. Cohorts A, B, C and D only: Have a PD-L1 positive tumor as determined by IHC at a central laboratory from either an archived formalin fixed paraffin embedded (FFPE) tumor sample or a newly obtained biopsy.
6. Have measurable disease based on RECIST 1.1. Tumor lesions situated in a previously irradiated area are considered measurable if progression has been demonstrated in such lesions.
7. Have a performance status of 0 or 1 on the ECOG Performance Scale.
8. Demonstrate adequate organ function as defined in [Table 1](#); all screening labs should be performed within 10 days of treatment initiation.

Table 1 Adequate Organ Function Laboratory Values

System	Laboratory Value
Hematological	
Absolute neutrophil count (ANC)	≥1,500 /mcL
Platelets	≥100,000 / mcL
Hemoglobin	≥9 g/dL or ≥5.6 mmol/L

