**Table 13** Operating Characteristics of Interim Analysis Rule for Head/Neck Cancer (HPV negative) and Urothelial Cancer– Pause Enrollment if  $\leq 1/10$  subjects respond

True ORR	Probability of Pausing Enrollment	Probability of Study Success
5%	0.91	<0.01
10%	0.74	0.02
15%	0.54	0.09
20%	0.38	0.25
25%	0.25	0.45
30%	0.15	0.65
35%	0.09	0.80
40%	0.05	0.90
45%	0.02	0.95

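### Do the unexplained differences between the head and neck null response rates (5%, 10% and 20%) require a change to the Cohort B2 and cetuximab/platinum tests?

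*Combined protocol and SAP*

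**What the plan says.** Section 8.2.7 sets three null rates for head and neck cancer.

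- **Cohort B, HPV negative: 10%.** With up to 22 evaluable subjects who are PD-L1 positive and "HPV negative head and neck cancer, the study has approximately 80% power to detect a 25% difference in ORR under the null hypothesis of ORR=10"%. Success is 6/22. No source is given for the 10%.
- **Cohort B, HPV positive: 20%.** "The null hypothesis rate of 20% is based on historic response of chemotherapy in head and neck cancer trials [37, 38"]. Success is 6 responses among up to 12 subjects.
- **Cohort B2: 5%.** "Success for this hypothesis requires at least 11/100 responses. The null hypothesis rate of 5% is based on historic response of chemotherapy", citing reference 37 alone.
- **Pooled cetuximab/platinum group from B and B2: 5%.** "Success for this hypothesis requires at least 8/60 responses. The null hypothesis rate of 5% is based on historic response of chemotherapy", again citing reference 37 alone.

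Under Section 8.2.6, if B2 succeeds, its one-sided 0.025 "will be passed to the secondary evaluation of subjects in Cohort B and Cohort B2 with prior exposure to cetuximab and platinum therapy".

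Section 5.1.2 gives both cohorts the same disease criterion: "Cohort B and B2: Have a diagnosis of squamous cell carcinoma of the head and neck". It adds: "Note: Cohort B2 will enroll both HPV positive and HPV negative subjects". Inclusion criterion 5 then separates them: PD-L1 positivity is required for Cohort B and not for B2. Section 8.1.3 repeats the null rates without a basis for any cohort; Section 8.1 describes itself as a short summary of 8.2.

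**The concern.** The 5% and the 20% are justified in the same words, as historical chemotherapy response in this disease, and share reference 37, yet one is four times the other. The 10% between them has no source. The obvious explanations do not close the gap.

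- **HPV status:** B2 mixes both HPV groups, and a mixture of a 10% and a 20% population cannot average 5%.
- **Prior treatment:** this might explain 5% in the cetuximab/platinum group, but B2 entry does not require either drug.
- **PD-L1 status:** the rationale in Section 4.2.1 concerns response to anti-PD-1 therapy, while the null is described as a chemotherapy rate.

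The plan is more explicit elsewhere. For Cohorts C and D, Section 8.2.7 names the drugs and the rates behind the null.

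At stake is the meaning of success in the largest cohort. The B2 hypothesis in Section 3.1 is that the response rate is clinically meaningful. If B2 can succeed at a rate that Cohort B's design takes as its null, a reader might credit B2 with clearing a bar it was never tested against.

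**Working it through.** **Inputs.** Sample sizes, cut-offs and null rates are from Section 8.2.7, the alpha rule from 8.2.6 and the interim table from 8.2.9.1. The tail probability is P(X ≥ r | n, p) = Σ C(n,k) p^k (1−p)^(n−k), summed over k = r to n.

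**1. Reproduce the plan's figures.**

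| Test | Rule | P(success) at null | One fewer response, at null | P(success) at 20% | Plan states |
|---|---|---|---|---|---|
| B2 | ≥11/100 | 0.0115 (5%) | 0.0282 | 0.9943 | >99% |
| Pooled | ≥8/60 | 0.0098 (5%) | 0.0297 | 0.9330 | 93% |

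Both cut-offs are the smallest that keep one-sided type I error at or below 0.025. For Cohort B HPV negative, P(X ≥ 6 | 22, 0.10) = 0.0182, or 0.0163 if an interim pause is treated as a stop. Table 13 ("Operating Characteristics of Interim Analysis Rule for Head/Neck Cancer (HPV negative) and Urothelial Cancer") gives 0.02, which matches either.

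**2. Behaviour at a true rate of 10%.**

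- B2: P(X ≥ 11 | 100, 0.10) = 0.417.
- Pooled group, ignoring the gate: P(X ≥ 8 | 60, 0.10) = 0.248.
- B2 and the gated test together: let m of the 60 come from Cohort B, so that 60−m are also in B2. Write A for responders among those 60−m, C for responders among the other 40+m B2 subjects, and D for responders among the m. The joint probability is P(A+C ≥ 11 and A+D ≥ 8). The plan does not give m. Taking every subject at 10%:

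| m | 0 | 8 | 20 | 34 |
|---|---|---|---|---|
| P(both succeed) | 0.219 | 0.199 | 0.174 | 0.148 |

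The value 34 is Cohort B's planned 22 + 12. It is not a hard limit, because the plan allows more to be enrolled.

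**3. Behaviour when B2 is truly at 5%.** B2 succeeds with probability 0.0115. Both tests succeed with probability 0.0034 to 0.0057, with Cohort B at its own nulls and m from 0 to 34. The gate holds.

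**4. What minimum success establishes** (exact Clopper-Pearson, already planned in Section 8.2.5.1).

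| Result | Estimate | 95% CI | One-sided p against 10% |
|---|---|---|---|
| 11/100 | 11.0% | 5.6% to 18.8% | 0.417 |
| 8/60 | 13.3% | 5.9% to 24.6% | 0.248 |
| 6/22 | 27.3% | 10.7% to 50.2% | 0.018 |

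Neither minimum result under the 5% null excludes 10%.

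**5. What moving to a 10% null would do.** B2 would need 17/100 (type I error 0.0206), and power at 20% would fall from 0.994 to 0.808. The pooled group would need 12/60 (type I error 0.0146), and power would fall from 0.933 to 0.551. A 20% null would equal the design alternative of both tests.

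**The case for a change.** The strongest case for acting is that the fix would be cheap. It asks only for a source for the 10%, a reason for the 5%, and a sentence reading the B2 and pooled intervals descriptively against 10%. None of this touches alpha, cut-offs or sample size. A trial whose hypothesis is a clinically meaningful response rate ought to say why the bar is lower in one head and neck cohort than in another.

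The documentary part stands. The rates differ, the wording behind two of them is identical, and no section explains the difference.

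The rest does not stand:

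- **A null belongs to its population.** The 10% was set for PD-L1 positive, HPV negative subjects with a 35% target. B2 enrols regardless of PD-L1 and HPV status, with a 20% target. Nothing in the plan calls 10% an absence of effect in that wider group. The PD-L1 difference does not itself justify a 5% chemotherapy rate, but it does mean the benchmark need not be the same number in both cohorts.
- **The 42% is an ordinary point on a power curve.** A valid test of 5% with 100 subjects should reject fairly often at 10%. Setting it beside 0.02 compares it with a test of a different null in 22 subjects.
- **Reading the intervals against 10% adds little.** The intervals will be reported anyway, so anyone can compare them with 10%. Writing that comparison into the plan would promote an unsourced figure, set for another population, to a reference for B2.
- **Which rate is right cannot be settled here.** It depends on references 37 and 38, whose contents the documents do not give.

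**Conclusion.** No change to the plan follows. The difference between the null rates is real and unexplained, but what is missing is rationale; the tests are sound. The 5% tests, their cut-offs, the step-down gate and the stated power are all correct for the null they name: type I error 1.1% and 1.0%, power 99.4% and 93.3% at a true rate of 20%. Adding the missing sentence would leave every decision and reported number as it is. Replacing 5% with 10% would cost about 19 points of power in B2 (0.994 − 0.808 = 0.186) and 38 in the pooled group (0.933 − 0.551 = 0.382), on the strength of a benchmark that has no source and belongs to a narrower population.

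The practical consequence is one of interpretation. Success at the minimum in B2 or in the pooled group shows a response rate above 5%, and should not be described as meeting the Cohort B benchmark. The planned exact intervals show this directly.

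The figures at a true 10% assume independent responses at a common rate. The joint figures (14.8% to 21.9%) also depend on the unstated number of pooled subjects who come from Cohort B. The conclusion depends on none of these.
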